6.4 Excluded Concomitant Medications and Procedures

The following medications and procedures are prohibited during the study:

Systemic treatment with any of the following metabolizing enzyme inhibitors is not permitted during this study. (A drug-drug interaction [DDI] with a strong inhibitor would increase ixazomib exposure and could lead to a higher probability of an AE.):.

- Strong inhibitors of CYP1A2: fluvoxamine, enoxacin, ciprofloxacin
- Strong inhibitors of CYP3A: clarithromycin, telithromycin, itraconazole, voriconazole, ketoconazole, nefazodone, and posaconazole

Systemic treatment with any of the following metabolizing enzyme inducers should be avoided unless there is no appropriate alternative medication for the patient's use. A DDI with a strong inducer would decrease MLN2238 exposure. (Rationale: Unlike with inhibitors, if there were to be a DDI with an inducer, ixazomib exposure would be less; therefore, there would be a reduced chance of an AE. However, there may be less chance for an antitumor effect, but that is not an absolute reason to be taken off ixazomib):

• Strong CYP3A inducers: rifampin, rifapentine, rifabutin, carbamazepine, phenytoin, and phenobarbital

The dietary supplements St John's wort and Ginkgo biloba are not permitted.

Confidential

The following procedures are prohibited during the study:

- Any antineoplastic treatment with activity against AML or MDS except for drugs in this treatment regimen.
- Radiation therapy (note that, in general, the requirement for local radiation therapy indicates disease progression).
- Platelet transfusions to help patients meet treatment criteria are not allowed within 3 days prior to study drug administration on any dosing day.

6.5 Permitted Concomitant Medications and Procedures

The following medications and procedures are permitted during the study:

- Antiemetics, including 5-HT3 serotonin receptor antagonists, may be used at the discretion of the investigator.
- Loperamide or other antidiarrheal should be used for symptomatic diarrhea at discretion of the investigator. The dose and regimen will be according to institutional guidelines. IVF should be given to prevent volume depletion.
- Growth factors (eg, granulocyte colony stimulating factor [G-CSF], granulocyte macrophage-colony stimulating factor [GM-CSF], recombinant erythropoietin) are permitted. Their use should follow published guidelines and/or institutional practice; however, alternative usage may be reviewed with the principal investigator. Erythropoietin will be allowed in this study. Their use should follow published guidelines and/or institutional practice.
- Patients should be transfused with red cells and platelets as clinically indicated and according to institutional guidelines.
- Antiviral therapy such as acyclovir may be administered if medically appropriate.
- Concomitant treatment with bisphosphonates will be permitted, as appropriate.
- Patients who experience worsening neuropathy from baseline may be observed for recovery, and have dose reductions/delays as indicated in the protocol, and any supportive therapy or intervention may be initiated as appropriate at the discretion of the investigator.

Confidential

• Supportive measures consistent with optimal patient care may be given throughout the study.

6.6 Precautions and Restrictions

- Fluid deficit should be corrected before initiation of treatment and during treatment.
- Nonsteroidal anti-inflammatory drugs (NSAIDs) should be avoided with impaired renal function given reported NSAID-induced renal failure in patients with decreased renal function.

Pregnancy

It is not known what effects ixazomib has on human pregnancy or development of the embryo or fetus. Therefore, female patients participating in this study should avoid becoming pregnant, and male patients should avoid impregnating a female partner. Nonsterilized female patients of reproductive age group and male patients should use effective methods of contraception through defined periods during and after study treatment as specified below.

Female patients must meet 1 of the following criteria:

- Postmenopausal for at least 1 year before the screening visit, OR
- Surgically sterile, OR
- If they are of childbearing potential, agree to practice 2 effective methods of contraception, at the same time, from the time of signing the informed consent form through 90 days after the last dose of study drug, AND
- Agree to practice true abstinence when this is in line with the preferred and usual lifestyle of the subject. (Periodic abstinence [eg, calendar, ovulation, symptothermal, post-ovulation methods] and withdrawal are not acceptable methods of contraception.)
- Two forms of barrier contraception: Females Diaphragm plus spermicide Males-Condom plusspermicide

Male patients, even if surgically sterilized (ie, status postvasectomy), must agree to 1 of the following:

- Agree to practice effective barrier contraception during the entire study treatment period and through 90 days after the last dose of study drug, OR
- Agree to practice true abstinence when this is in line with the preferred and usual lifestyle of the subject. (Periodic abstinence (eg, calendar, ovulation, symptothermal, post-ovulation methods] and withdrawal are not acceptable methods of contraception.)
- Two forms of barrier contraception: 1. Condom 2. Spermicide

6.7 Management of Clinical Events

Adverse drug reactions such as thrombocytopenia, diarrhea, fatigue, nausea, vomiting, and rash have been associated with ixazomib treatment. Management guidelines regarding these events are outlined below. Further details of management of ixazomib AEs are described in Section 6 of the ixazomib IB.

Prophylaxis Against Risk of Reactivation of Herpes Infection

Patients may be at an increased risk of infection including reactivation of herpes zoster and herpes simplex viruses. Antiviral therapy such as acyclovir, valacyclovir, or other antivirals may be initiated as clinically indicated. Other antivirals are also acceptable.

Nausea and/or Vomiting

Standard anti-emetics including 5-hydroxytryptamine 3 serotonin receptor antagonists are recommended for emesis if it occurs once treatment is initiated; prophylactic anti-emetics may also be considered at the physician's discretion. Dexamethasone should not be administered as an anti-emetic. Fluid deficit should be corrected before initiation of study drug and during treatment.

Diarrhea

Prophylactic antidiarrheals will not be used in this protocol. However, diarrhea should be managed according to clinical practice, including the administration of antidiarrheals once infectious causes are excluded. Fluid intake should be maintained to avoid dehydration. Fluid deficit should be corrected before initiation of treatment and during treatment.

Erythematous Rash With or Without Pruritus

As with bortezomib, rash with or without pruritus has been reported with ixazomib, primarily at the higher doses tested and when given with agents where rash is an overlapping toxicity. The rash may range from limited erythematous areas, macular and/or small papular

bumps that may or may not be pruritic over a few areas of the body, to a more generalized eruption that is predominately on the trunk or extremities. Rash has been most commonly characterized as maculopapular or macular. To date, when it does occur, rash is most commonly reported within the first 3 cycles of therapy. The rash is often transient, self-limiting, and is typically Grade 1 to 2 in severity.

Symptomatic measures such as antihistamines or corticosteroids (oral or topical) have been successfully used to manage rash and have been used prophylactically in subsequent cycles. The use of a topical, IV, or oral steroid (eg, prednisone ≤ 10 mg per day or equivalent) is permitted. Management of a Grade 3 rash may require intravenous antihistamines or corticosteroids. Administration of ixazomib (and/or other causative agent if given in combination) should be modified per protocol and re-initiated at a reduced level from where rash was noted (also, per protocol).

In line with clinical practice, dermatology consult and biopsy of Grade 3 or higher rash or any SAE involving rash is recommended. Prophylactic measures should also be considered if a patient has previously developed a rash (eg, using a thick, alcohol-free emollient cream on dry areas of the body or oral or topical antihistamines). A rare risk is Stevens-Johnson Syndrome, a severe and potentially life-threatening rash with skin peeling and mouth sores, which should be managed symptomatically according to standard medical practice. Punch biopsies for histopathological analysis are encouraged at the discretion of the investigator.

Thrombocytopenia

Blood counts should be monitored regularly as outlined in the protocol with additional testing obtained according to standard clinical practice. Thrombocytopenia may be severe but has been manageable with platelet transfusions according to standard clinical practice. Ixazomib administration should be modified as noted as per dose modification recommendations in the protocol when thrombocytopenia occurs (see Table 6-2). Therapy can be reinitiated at a reduced level upon recovery of platelet counts. A rare risk is thrombotic thrombocytopenic purpura (TTP), a rare blood disorder where blood clots form in small blood vessels throughout the body characterized by thrombocytopenia, petechiae, fever, or possibly more serious signs and symptoms. TTP should be managed symptomatically according to standard medical practice.

Neutropenia

Blood counts should be monitored regularly as outlined in the protocol with additional testing obtained according to standard clinical practice. Neutropenia may be severe but has

38

been manageable. Growth factor support is not required but may be considered according to standard clinical practice. Ixazomib administration should be modified as noted as per dose modification recommendations in the protocol when neutropenia occurs (see Table 6-2). Therapy can be reinitiated at a reduced level upon recovery of ANCs.

Fluid Deficit

Dehydration should be avoided since ixazomib may cause vomiting, diarrhea, and dehydration. Acute renal failure has been reported in patients treated with ixazomib, commonly in the setting of the previously noted gastrointestinal toxicities and dehydration.

Fluid deficit should be corrected before initiation of study drug and as needed during treatment to avoid dehydration.

Hypotension

Symptomatic hypotension and orthostatic hypotension with or without syncope have been reported with ixazomib. Blood pressure should be closely monitored while the patient is on study treatment and fluid deficit should be corrected as needed, especially in the setting of concomitant symptoms such as nausea, vomiting, diarrhea, or anorexia. Patients taking medications and/or diuretics to manage their blood pressure (for either hypo- or hypertension) should be managed according to standard clinical practice, including considerations for dose adjustments of their concomitant medications during the course of the trial. Fluid deficit should be corrected before initiation of study drug and as needed during treatment to avoid dehydration.

Posterior Reversible Encephalopathy Syndrome

One case of posterior reversible encephalopathy syndrome, which ultimately resolved, has been reported with ixazomib. This condition is characterized by headache, seizures and visual loss, as well as abrupt increase in blood pressure. Diagnosis may be confirmed by magnetic resonance imaging (MRI). If the syndrome is diagnosed or suspected, symptomdirected treatment should be maintained until the condition is reversed by control of hypertension or other instigating factors.

Transverse Myelitis

Transverse myelitis has also been reported with ixazomib. It is not known if ixazomib causes transverse myelitis; however, because it happened to a patient receiving ixazomib, the possibility that ixazomib may have contributed to transverse myelitis cannot be excluded.

6.8 Preparation, Reconstitution, and Dispensing

Ixazomib is an anticancer drug and as with other potentially toxic compounds caution should be exercised when handling ixazomib capsules.

6.9 Packaging and Labeling

The study drug ixazomib capsules will be provided by Millennium. The study drug will be labeled and handled as open-label material, and packaging labels will fulfill all requirements specified by governing regulations.

The capsules are individually packaged in cold form foil-foil blisters in a child-resistant carton. There are 3 capsules in each wallet/carton.

6.10 Storage, Handling, and Accountability

Upon receipt at the investigative site, ixazomib should remain in the blister and carton provided until use or until drug is dispensed. The container should be stored at the investigative site refrigerated (36°F to 46°F, 2°C to 8°C). Ensure that the drug is used before the retest expiry date provided by Millennium. Expiry extensions will be communicated accordingly with updated documentation to support the extended shelf life.

In countries where local regulations permit, ixazomib capsules dispensed to the patient for take-home dosing should remain in the blister packaging and refrigerated as noted above until the point of use. The investigative site is responsible for providing the medication to the patient in the correct daily dose configurations. Comprehensive instructions should be provided to the patient in order to ensure compliance with dosing procedures. Patients who are receiving take-home medication should be given only 1 cycle of medication at a time. Patients should be instructed to store the medication refrigerated (36°F to 46°F, 2°C to 8°C) for the duration of each cycle. Patients should be instructed to return their empty blister packs to the investigative site, rather than discarding them. Reconciliation will occur accordingly when the patient returns for their next cycle of take-home medication. Any extreme in temperature should be reported as an excursion and should be dealt with on a case-by-case basis.

Because ixazomib is an investigational agent, it should be handled with due care. Patients should be instructed not to chew, break, or open capsules. In case of contact with broken capsules, raising dust should be avoided during the clean-up operation. The product may be harmful by inhalation, ingestion, or skin absorption. Gloves and protective clothing should be worn during cleanup and return of broken capsules and powder to minimize skin contact.

The area should be ventilated and the site washed with soap and water after material pick-up is complete. The material should be disposed of as hazardous medical waste in compliance with federal, state, and local regulations.

In case of contact with the powder (eg, from a broken capsule), skin should be washed immediately with soap and copious amounts of water for at least 15 minutes. In case of contact with the eyes, copious amounts of water should be used to flush the eyes for at least 15 minutes. Medical personnel should be notified. Patients are to be instructed on proper storage, accountability, and administration of ixazomib, including that ixazomib is to be taken as intact capsules.

6.11 Study Compliance

Study drug will be administered or dispensed only to eligible patients under the supervision of the investigator or identified sub-investigator(s). The appropriate study personnel will maintain records of study drug receipt and dispensing.

6.12 Termination of Treatment and/or Study Participation

Patients will be informed that they have the right to withdraw from the study at any time for any reason, without prejudice to their medical care. The investigator also has the right to withdraw patients from the study for any of the following reasons:

- Adverse event that in the opinion of the investigator makes continued administration of ixazomib undesirable or unsafe
- Protocol violation that makes continued participation undesirable or unsafe
- Lost to follow-up
- Clinically significant progressive disease
- Study terminated
- Other

Confidential

At the time of withdrawal, all study procedures outlined for the End of Study visit should be completed. The primary reason for patient's withdrawal from the study should be recorded in the source documents and CRF.

6.13End of Study Visit:

Subjects will undergo an end of study visit at the time of discontinuation of ixazomib. Whenever possible, a laboratory analysis including CBC and serum chemistries along with a bone marrow aspirate and/or biopsy will be performed at this visit.

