3. STUDY ENDPOINTS

3.1 Primary Endpoints

The primary efficacy endpoint is relapse free survival (RFS), defined as the interval from the date of the achievement of CR/CRi to the date of first objective documentation of disease relapse or death from any cause. Subjects who are lost to follow-up without documented relapse, or are alive at last follow-up without documented relapse will be censored at the date of their last response assessment.

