7. STATISTICAL AND QUANTITATIVE ANALYSES

7.1 Statistical Methods

This is a phase II study of ixazomib in AML/MDS patients who have achieved CR/CRi after front-line or first salvage therapy. Up to 40 patients will be enrolled in the study with an estimated accrual rate of one patient per month. The additional follow up will be 12 months after the last patient enrolls in the study. The primary objective is to evaluate relapse-free survival (RFS). The study will monitor futility and toxicity.

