7.1.1 Determination of Sample Size and Futility Monitoring

Futility will be monitored for the study. We will monitor RFS using the methods of Thall et al. (2005), and we will stop enrolling patients to the study if we have reason to believe that the median RFS is less than that from the historical data, which is around 11 months. The trial will be stopped if Pr(lamda(E) > lamda(S) | data from the trial) < 0.05, where lamda(S) is the median RFS for standard treatment in the historical data with an inverse gamma distribution IG(123, 1342), which corresponds to a mean of 11 months and a standard deviation of 1 month, the corresponding 95%CI of (9.2, 13.1) months. The prior for lamda(E) is assumed to be IG(3.21, 24.31), corresponding to a mean of 11 months and a larger standard deviation of 10. Futility monitoring will start once 10 patients have been enrolled. Assuming an accrual rate of 1 per month and an additional follow-up of 12 months, the operating characteristics for the futility stopping rule under various true states are summarized in the following table 1, with results based on 5000 simulations.

Median OS (M)	Prob(Stop Early)	Mean No. of Patients
		(25%, 75%)
17	0.012	39.6 (40, 40)
14	0.036	39.1 (40, 40)
11	0.164	36.8 (40, 40)
8	0.673	28.2 (17, 40)

Table 1: Operating characteristics for futility monitoring

5	1	14.2 (10, 17)

Multc Lean V2.1 and OneArmTTE Version 4.1.1 were used for the trial design. The Department of Biostatistics will provide and maintain a website ("Clinical Trial Conduct": https://biostatistics.mdanderson.org/ClinicalTrialConduct/) for futility monitoring for each treatment arm on this study. The Clinical Trial Conduct website resides on a secure server, and access is gained through usernames and passwords provided to personnel responsible for enrolling patients and updating patient data. The website is accessed through a browser using secure socket layer (SSL) technology. Personnel responsible for enrolling patients on trials, which includes the principal investigator(s), research nurse(s), and data coordinator(s), will be trained by members of the Department of Biostatistics in the use of the trial website; the importance of timely updating of follow-up times and recording of events will be emphasized in training.

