7.1.8. Study Endpoints

Relapse-Free Survival (RFS):

Is defined as the interval from the date of enrollment to the date of first objective documentation of disease relapse or death from any cause. Subjects who are lost to follow-up without documented relapse, or are alive at last follow-up without documented relapse will be censored at the date of their last response assessment.

Overall Survival (OS):

Time from date of treatment start until date of death due to any cause.

Complete Remission (CR):

Peripheral counts: No circulating blasts, neutrophil count $\ge 1 \ge 1 \ge 10^{9}$ /L and platelet count $\ge 100 \ge 10^{9}$ /L Bone marrow: $\le 5\%$ blasts, no detectable auer rods, no extramedullary leukemia with normal maturation of all cell lines. Persistent dysplasia will be noted.

Complete remission with incomplete count recovery (CRi):

Defined as a morphologic complete remission but the ANC may be $<1 \ge 10^9$ /L or the platelet count may be $<100 \ge 10^9$ /L.

Time to discontinuation from treatment will be assessed as an estimate of treatment failure/tolerability and is defined as the interval from the date of enrollment to the date of discontinuation. Subjects who are ongoing in treatment at the time of study closure will be censored at the date of last visit.

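### RFS has two start dates, no scheduled off-treatment follow-up, and a censoring rule that can treat late events and late event-free time differently

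*Combined protocol and SAP*

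**What the plan says.** **Start date.** Section 3.1 defines RFS as the "interval from the date of the achievement of CR/CRi" to relapse or death. Section 7.1.8 has it "defined as the interval from the date of enrollment to the date of first objective documentation of disease relapse" or death. Inclusion criteria 5 and 6 require a documented CR/CRi before entry but set no maximum time from CR/CRi to enrollment. Section 7.1.1 compares RFS with a historical median of about 11 months and does not say when that clock starts.

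**Follow-up.** Section 7.1 states: "The additional follow up will be 12 months after the last patient enrolls in the study". Table 1 was simulated "Assuming an accrual rate of 1 per month and an additional follow-up of 12 months". On the monitoring website, Section 7.1.1 adds that "the importance of timely updating of follow-up times and recording of events will be emphasized in training".

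The procedures end sooner. The last column of the study calendar is End of Treatment, and the marrow schedule is counted in cycles. Section 6.13 states: "Subjects will undergo an end of study visit at the time of discontinuation of ixazomib". Section 6.12 lists among the reasons for withdrawing a patient from the study "Adverse event that in the opinion of the investigator makes continued administration of ixazomib undesirable or unsafe", so stopping the drug and leaving the study are not kept apart. After treatment, the documents describe collection only of SAEs (30 days, later if related), pregnancies, and new primary malignancies (at least three years).

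**Censoring.** Under both definitions, patients without documented relapse who are lost or alive at last follow-up "will be censored at the date of their last response assessment".

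**The concern.** This single-arm trial is read against one historical number, so the start, ascertainment and censoring of RFS largely decide the answer.

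- If Section 3.1 governs and time is simply counted from CR/CRi, every patient contributes time in which, by eligibility, no event could have been observed. That lengthens RFS and weakens the futility rule.
- Nobody is told when or how to look for relapse once ixazomib stops, although the design relies on follow-up to closure.
- The censoring rule separates the date to which events are counted from the date to which event-free time is counted. A relapse or death learned of after treatment is an event. A patient known to be well at the same later date can be censored back at about the end of treatment. If events reach the team more often than event-free assessments do, RFS is shortened and futility stopping becomes more likely.

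The first and third problems push in opposite directions, and the reported median would not show which had acted.

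**Working it through.** **Inputs.** 40 patients at 1 per month, with closure 12 months after the last enrollment (Sections 4.2, 7.1), so follow-up f runs from 12 to 51 months. Twelve 28-day cycles = 336/30.44 = 11.04 months (Section 4.1). Priors: IG(3.21, 24.31) for ixazomib and IG(123, 1342) for the standard. Futility stop if the posterior probability is below 0.05, from 10 patients (Section 7.1.1). RFS is taken as exponential. With d events and total time T, the posterior of the median is IG(3.21 + d, 24.31 + ln2·T).

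**1. Reproducing Table 1.** With every patient followed throughout, looks at each enrollment and then monthly to closure, stopping is 0.013 / 0.037 / 0.165 / 0.697 / 1.000 at medians 17 / 14 / 11 / 8 / 5. The plan states 0.012 / 0.036 / 0.164 / 0.673 / 1. With looks only at enrollments, the value at median 8 is about 0.62 to 0.64. The look schedule is not given, so that row matches only approximately. Table 1 therefore describes full follow-up from enrollment.

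**2. Start date.** Assume a gap of g months from CR/CRi to enrollment for every patient, without delayed entry. At true median 11 (from enrollment), expected events are Σ[1 − 2^(−f/11)] = 32.9, and ln2·T ≈ 11 × 32.9 = 362. The median of IG(a, b) is about b/(a − 1/3), so from enrollment (24.31 + 362)/(36.11 − 0.33) ≈ 10.8. Each month of gap adds ln2 × 40 = 27.7 to b, or 27.7/35.8 ≈ 0.77 months to the estimate. Simulation agrees:

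| Assumed gap (months) | Posterior median, true 11 | Futility stopping, true 8 (looks at each enrollment) |
|---|---|---|
| 0 (enrollment start) | 10.7 | 0.64 |
| 1 | 11.5 | 0.38 |
| 2 | 12.3 | 0.18 |
| 4 | 13.8 | 0.01 |

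**3. Clean stop at 12 cycles.** Expected events = 40 × [1 − 2^(−11.04/11)] = 20.0, against 32.9 with the Section 7.1 follow-up. The posterior median is still about 10.7 at true 11, provided that stopping is unrelated to relapse risk. Comparing like with like, the 95% interval at 20 events is wider than at 25 events by 9.29/8.37 = 1.11 (stated prior) or 9.95/8.85 = 1.12 (large-sample form). If an assumed 50% of patients were treated to 24 cycles, expected events would be 24.5.

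**4. Censoring rule.** All events up to 12 cycles are counted. The table varies which later information is captured (assumed shares):

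| Late events known | Event-free patients assessed to closure | Posterior median, true 11 | Posterior median, true 17 |
|---|---|---|---|
| all | all (full follow-up) | 10.7 | 16.1 |
| half | half (symmetric) | 10.7 | 15.9 |
| all | 80% | 10.4 | – |
| all | 50% | 9.9 | – |
| half | none | 9.7 | 13.2 |
| all | none | 9.0 | 11.9 |

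In the last two rows, coverage of the 95% interval is 0.93 and 0.86 at true 11, and 0.83 and 0.56 at true 17. Futility stopping at median 11 rises from about 0.15 to 0.20 and 0.29 with looks at each enrollment. With monthly looks after accrual, the all-known case gives 0.31.

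**The case against.** Follow-up is clearly intended: Section 7.1 gives its length, Table 1 uses it, and staff are trained to update follow-up times. A reader might infer that the trial plans no follow-up after treatment. The documents do not support that; what is missing is the schedule and method.

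A reader might also infer that the trial will yield only 20 events and miss a required 25. That does not follow either. Sections 4.1 and 4.3 allow treatment beyond 12 cycles for patients who start MRD positive or are benefiting, and Section 7.1.4 mentions 25 events conditionally, not as a target.

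The strongest objection concerns censoring. The rule refers to the last response assessment, not the last scheduled marrow, and outcome may also be assessed as clinically indicated. Off-treatment counts or marrows could therefore move the censoring date. This stands: incomplete capture does not bias the estimate merely by being incomplete, only if it is asymmetric, and the 9.7 to 9.0 range is a limiting case. What remains is that nothing written makes capture symmetric or says which off-treatment assessments count.

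On the start date, the statistical section uses enrollment, which fits the accrual-based simulation. If Section 7.1.8 governs, the upward bias does not arise. But Section 3.1 is the primary endpoint definition, and no rule of precedence is given. Malignancy reporting for three years implies some later contact, but not relapse assessment.

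**Conclusion.** The point holds, and the plan should be changed. The textual gaps are certain: two RFS start dates, an unstated start for the benchmark, no off-treatment relapse or survival schedule, and a censoring date that need not match the reach of event capture.

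The sizes depend on assumptions. The start-date effect (11.5 to 13.8 instead of 10.7 at true 11) assumes that Section 3.1 is applied without delayed entry, with the same gap of 1 to 4 months for everyone. The censoring effect ranges from essentially none with symmetric capture, through 10.4 to 9.9, to 9.7 to 9.0 in the limiting case. Ending observation cleanly at 12 cycles is mainly a loss of events and precision. All figures assume exponential RFS; the futility figures also depend on a look schedule that the plan does not state.

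**What to change.** 1. Use one RFS start date in Sections 3.1 and 7.1.8, matched to the historical 11-month figure, and state that figure's start date. Enrollment fits the Table 1 simulation. If CR/CRi is chosen, count time at risk from enrollment only (delayed entry) in both the posterior and the futility rule.
2. Censor event-free patients at the last date documented relapse-free on the same follow-up that captures events, and name the off-treatment assessments that count.
3. Add relapse and survival status after treatment to the calendar for all patients, to 12 months after the last enrollment, with a closing check at data cut-off. About every 3 months from records, contact and standard-of-care tests would be one option. Rename the Section 6.13 visit end of treatment, separate stopping ixazomib from study withdrawal in Section 6.12, and state that stopping ixazomib does not censor RFS.

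The cost is protocol wording plus about 70 to 135 chart reviews or contacts over the whole trial, depending on the true median and on early stopping; survival contacts after relapse are extra. One downside should be acknowledged in the protocol: relapse detection off treatment would be less intensive than the 3-cycle marrows on treatment, which may delay documented relapse.
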